5 STUDY OBJECTIVES AND ENDPOINTS

5.1 Objectives

Primary Objective

To investigate whether markedly ill, treatment resistant psychiatric patients, assumed to have an inflammatory aetiology for their symptoms and diagnosed with schizophrenia spectrum disorder (SSD), are improved after treatment with the immunomodulatory drug rituximab (anti-CD20 antibodies).

Secondary Objectives

- To examine whether baseline levels of inflammatory markers predict treatment response.
- To examine whether changes in inflammatory markers or B-cell depletion correlate with treatment response.
- To examine metabolic mediators prior and after treatment and if they correlate with treatment response.
- To examine whether there is a change in markers for gut permeability after treatment.
- To examine whether there is a change in cognition after treatment.
- To investigate the patients' experiences of the novel treatment with a qualitative content analysis.

To assess safety and tolerability of rituximab during treatment for SSD.

5.2 Outcomes

Primary outcome

The primary outcome measure is change in symptoms measured as change in PANSS score.

Secondary outcome

- Global improvement at week 20, according to a balanced assessment (mean value of three independent assessors: 1) The treating clinician, 2) The patient's self-assessment and 3) A next-of-kin) using the Clinical Global Impression-Improvement (CGI-I) scale (range 1-7; 1 representing "Very much improved").
- Change in Personal and Social Performance Scale (PCP) measuring overall disability
- Change from baseline up to week 20 of illness severity (CGI-S) assessed by the clinician
- Difference from baseline up to week 20 in inflammatory markers in blood (gene expression and proteins) in relationship to clinical response (CGI-I)
- Proportion of responders to treatment, i.e. rated as much or very much improved since baseline according to CGI-I assessed by three different informants: 1) The treating clinician, 2) The patient's self-assessment and 3) A next of kin. If the mean value of these three is below 2.5 then the patient will be regarded as a responder (representing much or very much improved since baseline).

- Safety and tolerability of rituximab during treatment for SSD measured with the questionnaire Any Adverse Reactions (AAR).

Other outcome measures

- B-cell depletion at week 5, and B-cell subpopulations at week 20 in relation to clinical response and baseline levels of B-cells
- Changes in cognitive functioning at 20 weeks:
 - Neuropsychological functioning assessed with e.g. visuospatial and executive tests
- Change from baseline on rating scales that measure psychiatric symptoms specific for each diagnosis (shown below) *during the past 2 weeks*
 - BOCS for measuring obsessive-compulsive symptoms
 - RAADS-R for measuring autistic symptoms
 - PANSS for measuring psychotic symptoms
 - BFCR to measure catatonic symptoms
 - HADS for measuring depressive and anxiety symptoms

Long-term outcomes

40 weeks follow-up:

Outcome measures for long term are identical to that used at 20 week.

Change in symptoms measured as change in PANSS score.

The secondary outcome measures are:

- Global improvement at week 20, according to a balanced assessment (mean value of three independent assessors: 1) The treating clinician, 2) The patient's self-assessment and 3) A next-of-kin) using the Clinical Global Impression-Improvement (CGI-I) scale (range 1-7; 1 representing "Very much improved").
- Difference from baseline up to week 40 in inflammatory markers in blood (gene expression and proteins) in relationship to clinical response
- Change in PSP, clinician administered version, measuring overall disability from baseline up to week 40
- Change from baseline up to week 40 of illness severity (CGI-S) assessed by the clinician
- Proportion of responders to treatment, i.e. rated as "Much improved" or "Very much improved" since baseline according to CGI-I
- Life quality measured with BBQ

Other outcome measures are:

- B-cell subpopulations at week 40 in relation to clinical response
- Changes in cognitive functioning at 40 weeks:

- Neuropsychological functioning assessed with e.g. visuospatial and executive tests
- Change from baseline on rating scales that measure psychiatric symptoms specific for each diagnosis (shown below) *during the past 2 weeks*
 - BOCS for measuring obsessive-compulsive symptoms
 - RAADS-R for measuring autistic symptoms
 - PANSS for measuring psychotic symptoms
 - BFCR to measure catatonic symptoms
 - HADS for measuring depressive and anxiety symptoms

Follow-up, 1 year after treatment start. Outcome is PANSS and CGI-I in relation to treatment and evaluated by the treating clinician, the patient's self-assessment and a next of kin.

Qualitative content analysis

At endpoint 1, after 20 weeks, a qualitative content analysis will be performed.

6 SELECTION AND WITHDRAWAL OF VOLUNTEERS

6.1 Inclusion Criteria

To be eligible for inclusion into this study, each patient must fulfil all of the following criteria:

- 1) Age: 18 to 40 years
- 2) Duration of psychiatric illness: exceeding 2 years
- 3) Rated "Markedly ill", "Severely ill" or "Among the most extremely ill patients" on the Clinical Global Impression – Severity scale (CGI-S)
- 4) Global Assessment of Functioning below 50
- 5) Current diagnosis according to Diagnostic and Statistical Manual for Mental Disorders, 5th edition (DSM-5) of SSD (schizophrenia spectrum disorder)
- 6) Treatment resistance, i.e. failing to remit despite adequate treatments
- 7) If female and with any risk for pregnancy: willing to use contraceptives.
- 8) If antipsychotic treatment is prescribed the plasma concentrations of the drug must be tested and shown to be within the therapeutic interval.
- 9) Subjects should be judged by the investigator to be lucid and oriented to person, place, time, and situation when giving the informed consent.
- 10) Immunoglobulin levels within the normal range

Treatment resistance is defined as poor general functioning (GAF<50) and minor or no persistent improvement from previous treatment attempts, according to the following specifications: At least 2 trials with different evidence-based drug treatments for schizophrenia and at least one from the second generation of anti-psychotic drugs. Both drugs should have been tested for a minimum of 4 months with adequate dosages. Clozapine must have been tested or considered not feasible

Fertile women will only be included in the study if they are using/agree to use adequate contraception during treatment with the study drug and for the following 12 months after the last treatment. Adequate contraception is defined as at least 1 of the following: 1) abstinence, 2) oral contraceptive (combined or progesterone alone), 3) implants of levonorgestrel, 4) estrogenic vaginal ring, 5) percutaneous contraceptive patches, 6) injectable progestogen, 7) intrauterine device (IUD) or 8) male partner sterilization. Non-fertile women are defined as any female that is surgically sterile (documented hysterectomy and/or bilateral oophorectomy or tubal ligation).

Participants with severe SSD may not be able to respond to all questions or fill out rating scales. However, we will then obtain independent information whether the patient is improved or not according to CGI-I and PANSS even though h/she may not be able to fill out rating scales. Thus our primary outcome measure can be used at all times regardless of the state of the patient.

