- 8) if antipsychotic treatment is prescribed the plasma concentrations of the drug must be tested and shown to be within therapeutic interval.
- 9) subjects should be judged by the investigator to be lucid and oriented to person, place, time, and situation when giving the informed consent.
- 10) immunoglobulin levels within the normal range

EXCLUSION CRITERIA

- 1) on-going immunomodulatory treatment
- 2) pregnancy or breast-feeding
- 3) weight below 40 kg
- 4) clinically relevant on-going infection
- 5) chronic infections
- 6) positive screening test for hepatitis B, C, HIV or tuberculosis
- 7) any change of psychotropic medication within the previous 4 weeks
- 8) "much" or "very much improved" already at baseline according to CGI-I i.e. scores of 1 or 2 by the clinician
- 9) severe heart failure (NYHA grade IV) or other severe heart disease or history of cardiac

arrhythmia or myocardial infarction

- 10) unable to make an informed decision to consent to the trial
- 11) in compulsory treatment
- 12) treatment with clozapine within the last 2 months
- 13) previous treatments with immunosuppressive agents
- 14) malignancy currently or within 2 years prior to inclusion

STUDY DESIGN

Open pilot study, in addition a qualitative study using content analysis approach.

Participants will be treated initially for 20 weeks and followed for 52 weeks.

STATISTICAL ANALYSIS

Determination of Sample Size

In this pilot study population of 12 participants is presumed to be large enough to determine any effect of rituximab.

Primary objective: Effect of rituximab on schizophrenia symptoms measured with PANSS

The primary outcome (as described in section 5.2) is difference between baseline and endpoint on PANSS scale. 40% reduction in the PANSS scale.

Analyses of laboratory data related to clinical response

Laboratory data will consist of: plasma protein concentrations and leukocyte mRNA expression values for a number of cytokines and related substances (inflammatory markers); total number of B-lymphocytes and number of cells from various B-cell subsets at week 5, 12 and 20, as measured through highly sensitive flow cytometry (HSFC); plasma proteins and lipids as measured through metabolomics analysis; and blood levels of markers for gut permeability.

In order to examine whether baseline characteristics can predict treatment response, baseline values of all these measurements will

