7.1.2. Rating scales and tests

If more than one clinician will assess the patients rating calibration training for obtaining agreement on scorings will be performed.

Due to the large data collection in combination with the severity of the disorder in these patients missing data will be unavoidable. We will try to avoid missing data by providing clarification if a patient cannot understand the meaning of a question. For each symptom rating scale the response rate is set at a minimum of 80 % of the questions. Isolated missing scores will be replaced with the individual mean.

Demographics

- Background data collection form
- Pans Data Collection Form provides information about inherited physical and psychiatric disorders within the family.

Diagnostic interviews

- Mini International Neuropsychiatric Interview (M.I.N.I. version 7) is a structured clinical interview for psychiatric disorders. In addition the childhood onset diagnoses from the M.I.N.I. kid version will be amended to the adult version of M.I.N.I. (66, 67)
- PsychoNeuroinflammatory Related Signs and Symptoms Inventory (PNISSI) in order to identify and measure symptoms related to neuro-inflammation and diagnose PANDAS and PANS (68)

Assessment of severity, improvement and quality of life

- Clinical Global Impression-Improvement scale (CGI-I) measures change of symptoms on a 7 point Likert scale. CGI-I will also be administered to the next-of-kin (69)
- Patient's Global Evaluation (PGE) provides a self-administered global measure of improvement on a 7 point Likert scale (70)
- Clinical Global Impression-Severity scale (CGI-S) provides a global measure of illness severity on a 7 point Likert scale (69)
- Global Assessment of Functioning (GAF) measures general disability and symptom burden (71)
- Personal and Social Performance Scale (PSP) (72). The PSP is a 100-point single-item rating scale, subdivided into 10 equal intervals. The ratings are based mainly on the assessment of patient's functioning in four main areas: 1) socially useful activities; 2) personal and social relationships; 3) self-care; and 4) disturbing and aggressive behaviours.
- Level 1 Cross-cutting symptom measure of global symptom severity is a patient or informant rated measure included in the DSM-5, which assesses mental health domains that are important across psychiatric diagnoses. It includes 13 domains. We will use it with the clinician's assistance for adults (73)

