8.2 Administration of study drugs

A MabThera dose of 1000 mg will be given as intra-venous infusion in 1000 ml physiological saline (0.9 %, any brand provided by the pharmacy). Before administration of MabThera all patients will be given pre-medication to prevent or reduce possible side effects from MabThera.

Premedication is delivered 1-2 hours prior to rituximab and consists of T. Paracetamol 1000 mg, T. Loratadine 10 mg and T. Betapred (Betamethasone) 0.5 mg x 12 p.o (dissolved in a glass of water) in order to reduce the incidence of infusion-related reactions.

Patients remain on their stabilized treatments with psychotropic drugs during the first phase (20 weeks) of the study.

MabThera will be administered on one single occasion.

The MabThera treatment is administrated at the Rheumatology clinic at Örebro University Hospital. Study staff at the department of Rheumatology will prepare the saline bag for each patient infusion, adding MabThera. All bags will be labelled with a study specific label (**Error! Reference source not found.**). Each bag for infusion will be prepared just in time for each visit.

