10 STATISTICS

10.1 Determination of Clinical response

There is no power calculation due to the nature of this study, a pilot study. If at least 2 patients improve significantly we aim to continue with a controlled study.

Primary outcome

Reduction in PANSS score (30 items) is the primary outcome. 40% reduction in PANSS is regarded as a treatment response.

Secondary outcomes

CGI-I score 1 or 2 which corresponds to much or very much improved at week 20 is regarded as response. Assuming a SD of 1 in our sample we will be able to detect differences between the means before and after treatment corresponding to 0.64 points on the CGI-I scale.

Changes in PSP and clinician rated CGI-S score between enrollment and week 20.

PSP gives a score between 0-100 for disability.

CGI-S is a clinician rated measure of overall clinical severity that is rated on a scale between 1 and 7. This measure also has a floor effect that affects healthy participants, for a person with no clinical complaints or problems (which is most people in a population) will get a score of 1. This floor effect is not relevant to our study population. The score 7, which indicates the highest level of severity is phrased as "Among the most extremely ill patients". This may be true to the patient group in the present study. However, since patients currently in need of compulsory care are excluded from the study, a ceiling effect of the measure is unlikely.

Repeated measures of the PSP and CGI-S will be analysed using a repeated measures ANOVA.

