10.2 Statistical methods and analytical plan

10.2.1 Primary objective: Improvement reflected in change in PANSS score

To investigate whether markedly ill, treatment-resistant, psychiatric patients according to our inclusion/exclusion criteria are significantly improved after treatment with the immunomodulatory drug rituximab (as addition to the patients' standard treatment).

We will analyse the clinical data on a modified intention-to-treat (ITT) definition basis, i.e. including treatment dropouts who received at least one dose of rituximab as well as completers. In addition, a completer-only analysis will be performed. *The primary outcome* is change in PANSS score, assessed by a clinician.

Secondary outcomes: CGI-I score (range 1-7). All CGI-I ratings are performed by three independent raters (the patient, his or her next of kin and a clinician). The mean value of these three values will be used as the patients' scores. If one of the values is missing, the mean will be calculated using only two values.

One secondary outcome is binary: the proportion of responders to treatment at week 20 (and similarly at week 40). Treatment response is defined as a mean value below 2.5 on the CGI-I (calculated as above), which corresponds to the scale step descriptors "much improved" or "very much improved". Non-response is defined as a mean CGI-I value of 2.5 or higher.

The continuous secondary outcome variables at the 20-week and 40-week end points (CGI-S, PSP, and diagnosis specific rating scales) will be included in analysis of covariance (ANCOVA) models, controlling for baseline measures and demographic variables.

Side-effects will be closely monitored and types, frequency, severity and seriousness will be reported.

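### The plan calls the primary outcome always usable and promises to analyse dropouts, but gives no rule for a missing week-20 PANSS, so by default the modified ITT analysis reduces to the completer analysis

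*Combined protocol and SAP*

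**What the plan says.** - **Availability of the outcome.** Section 6.1 accepts that some patients will be too ill to complete scales. It says independent information on CGI-I and PANSS will then be obtained, and concludes: "Thus our primary outcome measure can be used at all times regardless of the state of the patient".
- **Missing items.** Section 7.1.2 describes missing data as unavoidable in this population and adds: "For each symptom rating scale the response rate is set at a minimum of 80 % of the questions". Isolated gaps are filled with the patient's own mean. No scale is exempted, and nothing is said about a scale that falls below 80%.
- **Withdrawal.** Sections 6.3 and 7.2 let patients leave at any time and say that data up to that point will be used, but not how.
- **Primary outcome.** Section 10.1: "Reduction in PANSS score (30 items) is the primary outcome. 40% reduction in PANSS is regarded as a treatment response". The Synopsis describes it as the difference between baseline and endpoint. Section 10.2.1 says a clinician makes the rating.
- **Analysis sets.** Section 10.2.1 specifies a modified ITT analysis "including treatment dropouts who received at least one dose of rituximab as well as completers", plus a completer-only analysis. Completer is not defined.
- **Dosing.** Section 8.2: "MabThera will be administered on one single occasion".
- **Method.** No test or model is named for the primary PANSS change. Section 10.2.3 tests the psychiatric rating scales, among which Section 5.2 lists the PANSS, through week-20 scores and week-20-minus-baseline differences.
- **Patient-level missing values.** The only rule is for CGI-I, where two raters may stand in for three.

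**The concern.** A modified ITT analysis and a completer analysis are informative as a pair only if the first contains patients whom the second leaves out. Here the drug is given once, so after the infusion nobody can drop out of further treatment. The two sets can differ only in patients who left the study or missed the endpoint assessment. Those patients have no week-20 PANSS, and a week-20 difference cannot be computed for them.

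The sentence in Section 6.1 hides this, because it tells the reader that the problem cannot arise. With 12 patients and no control arm, losing even one or two can move the mean change noticeably, and no comparison group would share the loss.

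**Working it through.** **The plan's own figure.** The only precision statement concerns CGI-I: SD 1, detectable difference 0.64. It reproduces as t(0.975, 11 df)/√12 × 1 = 2.201/3.464 = 0.635. It assumes all 12 patients are scored. Nothing comparable is given for the PANSS.

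**Step 1: item rule.** 0.80 × 30 items = 24. Up to 6 missing items leave the minimum satisfied; with 7 or more it is not met, and the plan does not say what follows.

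**Step 2: who enters each analysis.** Let m be the number of the 12 dosed patients without a week-20 PANSS.
- Modified ITT as named: 12 patients.
- Modified ITT as computable from a week-20 difference: 12 − m.
- Completers, on the ordinary reading (PANSS available at the endpoint): 12 − m.

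The last two are the same patients for every m.

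**Step 3: possible size.** The documents give neither an SD for PANSS change nor a dropout rate, so the following are assumptions: changes normal, true mean 0, SD 12, n = 12, and in the worst case the m least-improved patients are the missing ones. A negative shift means apparent improvement. False improvement is one tail of a two-sided 5% one-sample t-test.

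| Missing | Shift in mean (points) | False improvement |
|---|---|---|
| 0 | 0 | 2.5% |
| 1 | −1.8 | about 8% |
| 2 | −3.3 | about 18% |

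The shift is proportional to the SD. A separate simulation at SD 15 gave −2.21 and −4.10, and multiplying by 12/15 returns −1.77 and −3.28. With two missing, the shift is −2.7 at SD 10 and −5.5 at SD 20. The false-improvement rate hardly depends on the SD.

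**Step 4: other mechanisms** (SD 15, 25% missing, or 3 of 12).
- Missingness unrelated to change: no bias.
- Moderate dependence (log-odds of being missing rise by 0.5 to 1 per SD of worse change): −1.8 to −3.2 points.
- The three worst missing: −5.9 points.
- The three most improved missing: +5.9 points.

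**Step 5: response proportion and go rule.** With two responders and three patients unscored, the 40% response rate is 2/9 = 22% among those scored and 2/12 = 17% if missing counts as non-response. The Section 10.1 rule for proceeding to a controlled study is a count of at least 2 improved patients, so missing patients make it harder to meet. At an assumed 10% response probability, the chance of meeting it falls from 34% with 12 scored to 23% with 9.

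**Step 6: how far a model on week 12 would help.** In the worst case of Step 3, a likelihood-based estimate that uses the week-12 change, with an assumed correlation of 0.5 to 0.8 between week-12 and week-20 change, leaves −1.4 to −0.7 points with one missing and −2.7 to −1.5 with two. It removes part of the shift, not all of it.

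**The case against.** Three stronger readings are tempting, and the documents support none of them.

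1. *The 80% rule leaves the PANSS unscored in the sickest patients.* The PANSS is clinician-rated, and Section 6.1 plans independent information for exactly these patients. The item rule follows a sentence about patients who do not understand a question, which suits self-report scales at least as well. No text says that a scale below 80% receives no total. What stands is an ambiguity: the rule exempts no scale, and the PANSS is listed in the same section. Withdrawal and missed visits are the firmer route to a missing score, and they alone defeat the claim in Section 6.1.

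2. *The plan prescribes a complete-case analysis.* It does not. Data up to withdrawal are to be used, and Table 1 schedules a week-12 PANSS, so carry-forward or a longitudinal model remains open. Complete-case is what results when a baseline-to-endpoint difference is computed with no further rule.

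3. *The result is biased towards improvement.* This depends on who goes missing. Entrants must be lucid at consent and not in compulsory care, and the investigator may remove patients who cannot comply, so a patient who cannot be assessed at week 20 may well have deteriorated. That makes the direction plausible. But Section 12.4 expects improvement chiefly in the most affected group, and losing those patients could bias the other way.

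It is also fair to say that the false-improvement rates refer to a PANSS test the plan never names, and that the stated go decision is a count which missing patients do not inflate.

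**Conclusion.** The point holds in a limited form. The availability claim in Section 6.1 conflicts with Sections 6.3, 7.1.2 and 7.2. Section 10.2.1 names an analysis set without a way to estimate the week-20 change in it, so by default its two analyses coincide and their agreement would show nothing.

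The consequence for the estimate is conditional. The shifts of about 1.8 and 3.3 points, and the false-improvement rates of about 8% and 18%, are a worst case under an assumed SD of 12, no true change, and loss of exactly the least-improved patients. Weaker dependence gives smaller shifts, independence gives none, and the reverse mechanism changes the sign. This is worth correcting before the data are seen because it concerns the primary outcome of a very small single-arm study. It does not show that the result will be too favourable.

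**What to change.** 1. Section 6.1: replace the availability claim with a statement that the PANSS is sought for every patient but may be missing after withdrawal or a missed visit.
2. Section 7.1.2: say whether the 80% minimum applies to the PANSS, and what happens to a scale that falls below it.
3. Section 10.2.1: define the modified ITT set as all dosed patients, and completers as those with a scorable week-20 PANSS.
4. Estimate the week-20 change with a likelihood-based repeated-measures model on the PANSS at weeks 0, 12 and 20. A patient with a week-12 score then contributes even without week 20.
5. For the 40% response, count patients without a week-20 PANSS as non-responders, with all dosed patients in the denominator.
6. Add a sensitivity analysis that gives missing patients zero change and then unfavourable change. This is essential: the model assumes data missing at random and cannot help patients lost before week 12. Zero alone is mild. In the worst case with two missing it moves the mean only from −3.3 to 10 × (−3.3)/12 = −2.75. Bringing the mean to zero would need an average worsening of 10 × 3.3/2 = 16.5 points in those two patients, so a range of unfavourable values should be shown.

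The cost is plan wording and one standard model; every visit is already scheduled. The downsides are a little more analysis, reliance on the week-12 score, and possibly a less favourable estimate.
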